12.0 Drug Accountability

Study drug may be dispensed only under the supervision of the investigator or delegate and only to study subjects. The pharmacist or designated site staff will maintain information regarding the dates and amounts of study drug received, dispensed to the subjects, and returned by the subjects. Subjects will be instructed to return all used and unused materials associated with the study drug to the site. These materials will be retained at the site.

13.0 Disposal

The site staff or pharmacy personnel will retain all materials returned by the subjects until the drug accountability has been performed. Following completion of drug accountability, all study drug materials may be destroyed at the site according to their institutional policies and or/SOP.s

14.0 Blinding and Unbinding

The study pharmacist in this study will be an unblinded pharmacist. Should an event occur requiring unblinding of the investigative team, the PI and the Co-I will confer. The unblinded pharmacist at that time may unblind the PI if it is deemed necessary.

15.0 Prohibited Medications and Other Restrictions

In vitro studies showed that ivacaftor is mainly metabolized by CYP3A4. In vivo, ketoconazole, a strong CYP3A inhibitor, when co-administered with a single 150-mg dose of Ivacaftor significantly inhibited the metabolism of ivacaftor, which resulted in significantly higher systemic exposure of ivacaftor (AUC increased to 8.5-fold and Cmax increased to 2.7-fold), confirming that Ivacaftor is a sensitive CYP3A substrate.³³ Based on this, moderate or strong inhibitors and inducers of CYP3A4 will not be allowed in this study. This includes grape fruit juice and Seville orange products.

16.0 Collection Period of Adverse Events

An adverse event is defined as any untoward medical occurrence in a subject during the study; the event does not necessarily have a causal relationship with the treatment. An adverse event can be any unfavorable and unintended sign (e.g., including an abnormal laboratory finding), symptom, or disease that occurs during the study, whether or not it is considered to be study drug related. This includes any newly occurring event or previous condition that has increased in severity or frequency after obtaining informed consent and assent (where applicable). Any abnormal findings in clinical laboratory assessments, ECGs, vital signs, or physical examination that are judged by the investigator to be clinically significant must also be reported as adverse events. Planned/elective hospital admissions or surgical procedures are not to be considered adverse events.

16.1 Documentation of Adverse Events

All subjects will be queried, using non-leading questions, about the occurrence of adverse events at each visit. In addition, all spontaneously reported adverse events will be collected. All adverse events will be recorded in the eCRF and source document. Adverse events should be reported and documented in accordance with the procedures outlined below. All adverse events occurring during the study must be documented in the relevant eCRF and source documents. The following data must be documented for each adverse event:

- Description of the event
- Classification of “serious” or “not serious”
- Date of first occurrence and date of resolution (if applicable)
- Severity (see Section 16.2 and Table 16-1)
- Causal relationship to study drug (see Section 16.3)
- Action taken (see Section 16.4)

- Outcome (see Section 16.5)
- Concomitant or other treatment given (see Section 16.6)

When possible, a constellation of signs and/or symptoms should be identified as one overall event or diagnosis.

Any adverse event judged by the investigator to be related to the study drug that is continuing at the Follow-up Visit will be followed until it has been resolved, returned to baseline, or become stable or a chronic condition.

16.2 Adverse Event Severity

The investigator must determine and record the severity of all serious and non-serious adverse events. The Common Terminology Criteria for Adverse Events (CTCAE) version 4.019 should be used for grading the severity of adverse events. Adverse events of CTCAE Grades 4 and 5 should be documented as “life-threatening” in the eCRF and source documents. In considering the severity of an adverse event in a pediatric subject, the investigator should consider that reference ranges for pediatric clinical laboratory parameters may differ from those given in the CTCAE. An adverse event that does not appear in the CTCAE should be determined according to the definitions in Table 16-1. A copy of the CTCAE will be provided as an attachment to the protocol.

Table 16-1 Grading of Adverse Event Severity

Mild (Grade 1)	Awareness of the event; may cause minimal interference with the subject's daily life.
Moderate (Grade 2)	Discomfort enough to cause a noticeable impact on the subject's daily life.
Severe (Grade 3)	Incapacitation or significant impact on the subject's daily life.
Life-Threatening (Grade 4)	Subject in immediate risk of death from the event as it occurs. It does not include an event that, if it were to occur in a more severe form, might cause death.

16.3 Adverse Event Causality

The investigator will assess the relationship of the adverse event, if any, to the study drug. Causality should be classified using the categories presented in Table 16-2.

Table 16-2 Classifications for Adverse Event Causality

Related	Event follows a reasonable temporal association from administration of study drug without significant alternative etiology. May be supported by improvement upon study drug discontinuation and/or a positive re-challenge.
Possibly Related	Event follows a reasonable temporal association from administration of study drug and may have been produced by the

subject's clinical state or other factors. Information on drug withdrawal (dechallenge) may be lacking or unclear.

Unlikely Related	Event may or may not follow a clear temporal association with study drug administration and is probably produced by the subject's clinical state or other factors. Also includes clinical events for which there is insufficient information or contradictory information which prohibits a proper assessment.
Not Related	No relationship between the event and administration of the study drug.

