16.4 Study Drug Action Taken

The investigator will classify the study drug action taken with regard to the adverse event. The action taken should be classified according to the categories shown in Table 16-3.

Table 16-3 Classifications for Study Drug Action Taken with Regard to an Adverse Event

Drug Interrupted	Study drug administration stopped in response to an adverse event. If study drug administration is not re-started, this action changes to "drug withdrawn."
Drug Withdrawn	Study drug administration permanently discontinued in response to an adverse event.
Dose Not Changed	Study drug dose not changed in response to the adverse event.
Not Applicable	Action taken regarding study drug administration does not apply. "Not applicable" should be used in circumstances such as when the subject has died, or the investigational treatment had been completed before the adverse event, or adverse event occurred before the investigational treatment started
Unknown	Action taken is unknown, e.g., a subject hospitalized at a hospital not under the care of the investigator and the investigator has no knowledge whether study drug was continued or not.

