16.8 Elevation of Liver Function Test Parameters

Subjects with new ALT or AST elevations of $>3 \times$ ULN and clinical symptoms be followed closely, including repeat confirmatory testing within 48 to 72 hours of the initial finding and subsequent close monitoring of ALT and AST level, as clinically indicated.

Study drug administration will be interrupted immediately and the DSMB Chair will be notified if any of the following criteria is met:

- ALT or AST $>8 \times$ ULN
- ALT or AST $>5 \times$ ULN for more than 2 weeks
- Total bilirubin $>2 \times$ ULN and/or clinical jaundice, in association with elevation of ALT or AST $>3 \times$ ULN

A thorough investigation of potential causes should be conducted and the subject will be followed closely for clinical progression.

If no convincing alternative etiology (e.g., viral hepatitis, alcohol ingestion) for the elevated transaminases is identified, regardless of whether ALT or AST levels have improved, the subject will be discontinued from the study, in consultation with the Medical Monitor

An early termination visit should be scheduled as soon as possible. In addition to the early termination visit assessments specified in the protocol, a blood sample should be obtained for pharmacokinetic analysis. Subjects discontinued for elevated transaminases should be followed until their transaminases normalize or return to baseline. If a convincing alternative etiology for the elevated transaminases is identified and the subject's symptoms and laboratory findings have improved, the investigator will consider resuming study drug treatment in consultation with the PI.

16.9 Definition of COPD Exacerbation.

We will monitor the incidence and severity of COPD exacerbations to measure safety of ivacaftor and estimate whether a reduction in COPD exacerbations is plausible with effective CFTR potentiation by ivacaftor, and to develop sample size estimates for future studies. For the purposes of this protocol, COPD exacerbations will be defined as follows: a complex of respiratory symptoms (increase or new onset) of more than one of the following: cough, sputum, wheezing, dyspnea, or chest tightness, requiring treatment with antibiotics and/or systemic steroids for at least three days.

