17.0 Ongoing Safety Monitoring during the Trial

The PI is primarily responsible for reviewing safety data which will be monitored on a continual basis throughout the performance of the study as well as conducting interim safety analyses 10, 20, and 30 study subjects have completed 84 days of the study (see *Safety Monitoring* and *Interim Safety Analysis* below).

The PI will monitor and provide recommendations concerning safety and tolerability based on his/her evaluation of emerging trends and risks in reported SAEs and AEs which capture abnormal vital signs, physical exam findings, and abnormal laboratory tests.

The PI will review all SAEs in real time and conduct appropriate reporting to the IRB and Vertex Pharmaceuticals as required, within 24 hrs at maximum.

The PI will make the following determinations with the site Investigator reporting the SAE:

- Does the reported adverse event meet one of the FDA's definitions for serious?
- Is the event unexpected?
- Is the event related to study drug?

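### Table 16-2 codes unassessable adverse events as Unlikely Related, and Section 16.1 requires no follow-up of them past the last visit, even when they are serious

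*Combined protocol and SAP*

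**What the plan says.** Section 16.3 has the investigator classify each event with Table 16-2, whose four classes are Related, Possibly Related, Unlikely Related and Not Related. Unlikely Related is for an event that "is probably produced by the subject's clinical state or other factors", with or without a clear temporal link to dosing. The same entry then adds: "Also includes clinical events for which there is insufficient information or contradictory information which prohibits a proper assessment". The scale has no class for unknown or unassessable causality.

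Section 16.1 ties follow-up after the last visit to the causality judgement: "Any adverse event judged by the investigator to be related to the study drug that is continuing at the Follow-up Visit will be followed". The stated end point is resolution, return to baseline or a stable state. The section does not say which of the four classes count as related. Section 16.8 has one further open-ended rule: "Subjects discontinued for elevated transaminases should be followed until their transaminases normalize or return to baseline". Section 17.0 has the PI review all SAEs in real time and answer, among other questions, "Is the event related to study drug", again with no link to the four classes.

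Other provisions do not depend on causality. Section 16.0 defines an adverse event "whether or not it is considered to be study drug related". Section 16.1 states: "All adverse events will be recorded in the eCRF and source document". Table 16-4 (Section 16.5) has an outcome code for events still continuing. Section 6.0 makes safety the primary outcome, analysed descriptively. The interim report in Section 18.1 lists adverse events with no causality filter.

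**The concern.** Lack of information about cause is not evidence against the drug, but Table 16-2 gives both the same code. A reader of the final causality table could not tell how many Unlikely Related events were judged so on evidence and how many were never assessable.

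The follow-up rule makes this worse. Later information such as hospital records, resolution or recurrence could move an unassessable event into an informative class, yet the code it receives takes it outside the one general rule that would require anyone to collect that information. At stake are the causality tabulation and the final outcome of ongoing serious events, in a trial whose primary outcome is safety.

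**Working it through.** The documents give no figure on this point, so there is nothing to recompute. The check sets the provisions side by side.

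**Step 1: can unassessable events be identified in the data?** Section 16.1 lists the data items required for each event. Causality is one, coded by Table 16-2. None of the listed items records why a class was chosen. An unassessable event and an event judged probably due to the underlying disease both appear as Unlikely Related, so the code alone cannot separate them. Table 16-3 handles the same problem differently: it has an Unknown class for the action taken with study drug.

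**Step 2: does Section 16.1 require follow-up of such an event past the Follow-up Visit?** The word related is not mapped to Table 16-2, so each possible reading is tried.

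| Class in Table 16-2 | Reading A: Related only | Reading B: Related and Possibly Related | Reading C: all except Not Related |
|---|---|---|---|
| Related | required | required | required |
| Possibly Related | not required | required | required |
| Unlikely Related (holds the unassessable events) | not required | not required | required |
| Not Related | not required | not required | not required |

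Readings A and B both leave unassessable events out. Reading C would include them, but only by treating an event classed as unlikely to be related as one judged related. The text does not say this.

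**Step 3: does another rule cover the gap?** Section 16.8 does so for subjects discontinued for elevated transaminases, with no relatedness condition in its wording. Section 17.0 covers all SAEs, but its rule is real-time review and reporting, not continued follow-up to an outcome. No section requires follow-up of ongoing serious events regardless of causality.

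**Step 4: when does required follow-up end?** The synopsis sets the Follow-up Visit at 14 ± 7 days after the last dose, so 14 − 7 = 7 to 14 + 7 = 21 days. Table 1 sets it at Day 98 ± 2. With a last dose on Day 84, that is 98 − 84 = 14, so 12 to 16 days. Section 7.0 asks subjects who stop treatment early to return about 4 weeks after the last dose. The gap in Step 2 opens after whichever of these visits applies.

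**Step 5: what is not affected?** Sections 16.0 and 16.1 capture every event whatever its class, Table 16-4 lets it be coded as continuing, and no section filters the summaries by causality. An all-causality count by arm is the same however an event is classified.

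**The case against.** The strongest defence is that nothing is lost from the main safety comparison. The trial is double-blind and placebo-controlled, both arms use the same scale, all events are recorded, all SAEs get real-time PI review, and the analysis is descriptive with no causality filter. All of this stands, and it confines the problem to the causality tabulation and late outcome data. It does not remove it. With about 10 placebo subjects the arm comparison is thin: zero events in 10 has a one-sided 95% exact upper bound of 1 − 0.05^(1/10) = 0.26. Event-level causality and outcome therefore carry some weight. That bound describes the small placebo arm, not the size of this defect.

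Three stronger readings are tempting, and the documents do not support them.

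- A reader might infer that unassessable events are counted as non-drug. No section collapses the four classes into two. The yes/no question in Section 17.0 makes a negative answer for an Unlikely Related event possible but does not prescribe it.
- A reader might infer that these events are dropped. They stay in the eCRF with an outcome code. Only required follow-up past the last visit is missing.
- A reader might take the example in Table 16-3, "a subject hospitalized at a hospital not under the care of the investigator", as an event bound to be coded Unlikely Related. That entry concerns the action taken with study drug, not causality. Possibly Related in Table 16-2 expressly allows for missing or unclear dechallenge information and fits at least as well. The overlap shows only that two classes compete for poorly documented events.

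**Conclusion.** The point holds in a limited form. Table 16-2 merges unassessable events with events judged unlikely to be due to the drug. Section 16.1 does not say which classes count as related and, on either natural reading, requires no follow-up of ongoing unassessable events past the Follow-up Visit, including serious ones. The transaminase rule in Section 16.8 is the only exception found.

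No percentage-point size can be given. One reclassified subject among about 30 on ivacaftor is 1/30 = 3.3 points, and a reader might take that as the bias in a related-event rate. The plan specifies no such rate, and the documents do not say how many events would be unassessable. Nor do they support a claim that few events will be classed Related.

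The conclusion assumes that related in Section 16.1 means Related, alone or with Possibly Related. If the sponsor intended every class except Not Related, the follow-up gap closes for unassessable events, but the merged class remains and the wording still needs to say so. Investigators may also follow such events voluntarily; the point concerns what is required.

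**What to change.** 1. In Table 16-2, remove the sentence on insufficient or contradictory information from Unlikely Related and add a fifth class, Not assessable. Tabulate it on its own line, beside all-causality adverse events by arm. A separate line is preferable to pooling with Possibly Related, which would replace one default with the opposite one.
2. State in Sections 16.1 and 17.0 which classes count as related for follow-up and for the SAE determination.
3. Extend follow-up past the last visit in Section 16.1 to all ongoing serious events regardless of causality, and to ongoing events classed Related, Possibly Related or Not assessable. Allow the class and outcome to be updated when information arrives.

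The cost is one extra eCRF option and a few follow-up calls or record requests. No visit, procedure or sample-size change is needed.

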16.4 Study Drug Action Taken

The investigator will classify the study drug action taken with regard to the adverse event. The action taken should be classified according to the categories shown in Table 16-3.

Table 16-3 Classifications for Study Drug Action Taken with Regard to an Adverse Event

Drug Interrupted	Study drug administration stopped in response to an adverse event. If study drug administration is not re-started, this action changes to "drug withdrawn."
Drug Withdrawn	Study drug administration permanently discontinued in response to an adverse event.
Dose Not Changed	Study drug dose not changed in response to the adverse event.
Not Applicable	Action taken regarding study drug administration does not apply. "Not applicable" should be used in circumstances such as when the subject has died, or the investigational treatment had been completed before the adverse event, or adverse event occurred before the investigational treatment started
Unknown	Action taken is unknown, e.g., a subject hospitalized at a hospital not under the care of the investigator and the investigator has no knowledge whether study drug was continued or not.

16.5 Adverse Event outcome

The investigator will document the outcome of the adverse event using the categories shown in Table 16-4.

Table 16-4 Classifications for Outcome of an Adverse Event

Recovered/Resolved	Resolution of an adverse event with no
---------------------------	--

	residual signs or symptoms.
Recovered/ Resolved With Sequelae	Resolution of an adverse event with residual signs or symptoms.
Not Recovered/ Not Resolved (Continuing)	Either incomplete improvement or no improvement of an adverse event, such it remains ongoing.
Fatal	Outcome of an adverse event is death. “Fatal” should be used when death is at least possibly related to the adverse event.

16.6 Clinically Significant Abnormal Study Assessments

A clinically significant worsening from baseline of any abnormal study assessment, such as laboratory test, ECG, physical examination, and vitals signs, should be considered an adverse event and recorded accordingly. If possible, a diagnosis for the clinically significant study assessment should be provided by the investigator (e.g., urinary tract infection or anemia). In the absence of a diagnosis, the abnormal study assessment itself is listed as the adverse event (e.g., bacteria in urine or decreased hemoglobin).

An abnormal study assessment is considered clinically significant if the subject has 1 or more of the following:

- Concomitant signs or symptoms related to the abnormal study assessment
- Further diagnostic testing or medical/surgical intervention
- A change in the dose of study drug or is discontinued from the study

Repeat testing to determine whether the result is abnormal, in the absence of any of the above criteria, does not necessarily meet clinically significant criteria.

16.7 Treatment Given

The investigator will describe whether any treatment was given for the adverse event. “Yes” is used if any treatment was given in response to an adverse event, and may include treatments such as other medications, hospitalization, surgery, or physical therapy. “No” indicates the absence of any kind of treatment for an adverse event.

16.8 Elevation of Liver Function Test Parameters

Subjects with new ALT or AST elevations of $>3 \times$ ULN and clinical symptoms be followed closely, including repeat confirmatory testing within 48 to 72 hours of the initial finding and subsequent close monitoring of ALT and AST level, as clinically indicated.

Study drug administration will be interrupted immediately and the DSMB Chair will be notified if any of the following criteria is met:

- ALT or AST $>8 \times$ ULN
- ALT or AST $>5 \times$ ULN for more than 2 weeks
- Total bilirubin $>2 \times$ ULN and/or clinical jaundice, in association with elevation of ALT or AST $>3 \times$ ULN

A thorough investigation of potential causes should be conducted and the subject will be followed closely for clinical progression.

If no convincing alternative etiology (e.g., viral hepatitis, alcohol ingestion) for the elevated transaminases is identified, regardless of whether ALT or AST levels have improved, the subject will be discontinued from the study, in consultation with the Medical Monitor

An early termination visit should be scheduled as soon as possible. In addition to the early termination visit assessments specified in the protocol, a blood sample should be obtained for pharmacokinetic analysis. Subjects discontinued for elevated transaminases should be followed until their transaminases normalize or return to baseline. If a convincing alternative etiology for the elevated transaminases is identified and the subject's symptoms and laboratory findings have improved, the investigator will consider resuming study drug treatment in consultation with the PI.

16.9 Definition of COPD Exacerbation.

We will monitor the incidence and severity of COPD exacerbations to measure safety of ivacaftor and estimate whether a reduction in COPD exacerbations is plausible with effective CFTR potentiation by ivacaftor, and to develop sample size estimates for future studies. For the purposes of this protocol, COPD exacerbations will be defined as follows: a complex of respiratory symptoms (increase or new onset) of more than one of the following: cough, sputum, wheezing, dyspnea, or chest tightness, requiring treatment with antibiotics and/or systemic steroids for at least three days.

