- Uncontrolled Diabetes
- Recent (e.g 1year) arterial thrombotic events (peripheral arterial disease, thrombotic stroke)
- Clinically significant arrhythmias requiring anti-arrhythmic agent(s) or conduction abnormalities that in the opinion of the investigator that affect patient safety such as the abnormalities listed below (patients with stable coronary artery disease are eligible)
 - ♦ Angina symptoms
 - ♦ History of MI
 - ♦ Revascularization procedure in the last year prior to screening
 - ♦ Clinically significant congestive heart failure (known LVEF $\leq 45\%$, cor pulmonale, diastolic heart failure, etc)

Investigational Drug: Ivacaftor, 150 mg PO every 12 hrs (or matching placebo)

Schedule of Study Visits: The first dose of ivacaftor will be administered at the Day 1 visit. Ivacaftor will be taken twice daily, with 12 hours between each dose from day 1 through the morning dose of day 84. Study visits will occur at Screening (-28 to -1 days), Day 1, Day 28 (\pm 7), Day 56 (\pm 7), Day 84 (\pm 7), and Follow-up (14 \pm 7 days after the last dose of ivacaftor).

Outcome Measures:

Safety assessments: Assessments include tests used in clinical studies to monitor the safety of ivacaftor in CF, including adverse event reporting, clinical laboratory testing, physical exams, and spirometry. The PI will review all SAEs in real time and conduct appropriate reporting to the FDA and IRB, as required, within 24hrs at maximum. Interim safety analysis will include review of AEs and safety labs by the PI and will be conducted after completion of approximately 10, 20, and 30 subjects. Ocular exam will be performed at baseline unless known history of cataracts.

PK: PK/PD analyses between ivacaftor levels and CFTR activity in the sweat gland will reveal new insights into the degree that wild-type CFTR can be activated. Calculated PK parameters include: area-under-the-curve (AUC₁₂), maximum plasma concentration (C_{max}), time to C_{max} (T_{max}), oral clearance (CL/F), terminal apparent distribution volume (V_z/F), and elimination half-life (t_{1/2}). Subsequently, intensive data and sparse plasma concentrations will be combined to create a population PK model to assess covariates, such as age, weight, sex, smoking status, etc. as previously conducted by our group for NIH and industry sponsored studies.

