7.0 Removal of Subjects in the Study

A subject may be discontinued from the study at any time if the subject, or investigator determines that it is not in the best interest of the subject to continue participation. A subject who prematurely discontinues treatment will be asked to return for a follow-up visit approximately 4 weeks following administration of the last dose of ivacaftor.

A subject will be discontinued from the study for any of the following reasons:

- A female subject has a confirmed pregnancy or, in the case of a male subject, his female partner becomes pregnant.
- A subject experiences an arrhythmia or conduction abnormality including, but not limited to, prolonged QTcF interval, where the severity is categorized as CTCAE version 4.0 Grade 3 or higher.
- A subject experiences MI/unstable angina or stroke/Cerebrovascular accident

A subject experiences

- an elevated alanine transaminase (ALT) or aspartate transaminase (AST) of $>8 \times \text{ULN}$ or
- ALT or AST $>5 \times \text{ULN}$ for more than 2 weeks or
- total bilirubin $>2 \times \text{ULN}$ and/or clinical jaundice, in association with elevation of ALT or AST $>3 \times \text{ULN}$ and no convincing alternative etiology (e.g., viral hepatitis, alcohol ingestion) for the Elevated transaminase is identified, regardless of whether ALT or AST levels had improved

A subject may be discontinued from the study for any of the following reasons:

- A subject develops a medical condition that requires prolonged concomitant therapy with a prohibited medication.
- A subject experiences a prolonged interruption of study drug.
- A subject develops a life-threatening adverse event, or a serious adverse event (SAE) that places them at immediate risk.
- A subject is noncompliant with study requirements.

- A subject experiences an increase in liver function tests (LFTs) to $3 \times$ ULN (if the baseline LFTs are normal) or an increase that exceeds an absolute value of $5 \times$ ULN

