11.0 Study Drug Supply, Storage and Handling

Ivacaftor tablets must be stored at room temperature, 15-30 degrees Celsius. While at the site, ivacaftor must be stored in a secure, temperature-monitored area of limited access. On day 1 a 28 day supply (+/-2 days) supply of ivacaftor will be dispensed to the subject. The drug will be dispensed an additional 28 day supply at day 28 and 56, with all drug being returned to the site at the day 84 visit.

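### Section 16.8 mandates no triggered repeat liver test for an asymptomatic ALT/AST of >5 to 8 × ULN, so the mandatory 2-week stopping rule may go unassessed until about 14 days after it is met

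*Combined protocol and SAP*

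**What the plan says.** Section 16.8 opens with a retest rule for new ALT or AST elevations above 3 × ULN "and clinical symptoms be followed closely, including repeat confirmatory testing within 48 to 72 hours of the initial finding". The rest of that sentence leaves further monitoring to clinical indication and gives no interval.

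The section then says: "Study drug administration will be interrupted immediately and the DSMB Chair will be notified if any of the following criteria is met". There are three criteria: ALT or AST above 8 × ULN; ALT or AST above 5 × "ULN for more than 2 weeks"; and bilirubin above 2 × ULN and/or jaundice together with ALT or AST above 3 × ULN. Section 7.0 puts the same three on its list of mandatory discontinuations.

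The discretionary list in Section 7.0 has a further liver item, beginning "A subject experiences an increase in liver function tests (LFTs) to". It permits discontinuation at 3 × ULN when baseline is normal, or above an absolute 5 × ULN. It requires no retest.

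Table 1 (Section 4.0) schedules safety labs at screening and Days 28, 56 and 84, and at follow-up only where indicated. Table 1 gives ±2 days around these visits. The synopsis, in the passage beginning "Study visits will occur at Screening (-28 to -1 days), Day 1, Day 28", gives ±7. Dosing runs "from day 1 through the morning dose of day 84".

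**The concern.** Of the three mandatory liver criteria, only the 2-week one needs more than one result. It runs on a 14-day clock, while the scheduled labs are 28 days apart. The one provision that would supply an earlier value is conditioned on symptoms, and an isolated transaminase rise may cause none.

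Followed as written, with no use of discretion, the plan lets a subject who has met a mandatory stopping criterion keep taking study drug because no test has been done to show it. Safety is the primary outcome, so the tests needed to apply a mandatory safety rule should be mandatory too.

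**Working it through.** The plan states no figure on this point, so there is nothing to reproduce. The check is date arithmetic.

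**Inputs**
- On-treatment safety labs: Days 28, 56 and 84 (Table 1).
- Visit windows: ±2 days (Table 1) or ±7 days (synopsis).
- Duration criterion: more than 14 days (Sections 16.8 and 7.0).
- Dosing: every 12 hours, 2 doses per day (synopsis, Section 9.0). One bullet in Section 4.0 describes a single morning dose; on that reading the dose counts below halve.
- Supply: "On day 1 a 28 day supply (+/-2 days) supply of ivacaftor will be dispensed to the subject" (Section 11.0), with further 28-day supplies at Days 28 and 56. Read as at most 28 + 2 = 30 days per dispensing.

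**Assumptions.** The clock starts at the first lab above 5 × ULN. The value stays >5 to 8 × ULN. There are no symptoms or jaundice, bilirubin is at or below 2 × ULN, and nobody orders an unscheduled test.

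**Formulas.** Gap between labs = 28 days, minus or plus twice the window. Excess = gap − 14. Doses = 2 × excess.

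| | Nominal | ±2 days | ±7 days |
|---|---|---|---|
| Gap to next required lab (days) | 28 | 28 − 4 to 28 + 4 = 24–32 | 28 − 14 to 28 + 14 = 14–42 |
| Excess past 14 days | 14 | 10–18 | 0–28 |
| Doses, ignoring supply | 28 | 20–36 | 0–56 |
| Doses, with the supply limit | 28 | 20–32 | 0–32 |

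**Supply limit.** A 30-day supply ends 30 − 14 = 16 days past the threshold, and 16 × 2 = 32 doses. Only left-over tablets could exceed this. Section 4.0 has subjects bring all remaining drug to each visit, and Section 12.0 keeps returned material at the site, so 32 is the sensible maximum.

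**Lower extreme.** With ±7 windows and a 14-day gap, the condition of more than 2 weeks is not yet met, so that lab could not trigger the rule.

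**Where the rule can act on scheduled labs alone**
- First seen at Day 28: confirmed at Day 56, so the rule can still shorten dosing.
- First seen at Day 56: confirmed at Day 84, when dosing ends anyway.
- First seen at Day 84: dosing is already over.

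The rule can therefore shorten dosing for only one of the three on-treatment labs.

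**With a required test at day 15.** The decision comes 28 − 15 = 13 days earlier nominally, 24 − 15 = 9 to 32 − 15 = 17 days earlier with ±2, and up to 42 − 15 = 27 days earlier with ±7. Because of the supply limit, at most 30 − 15 = 15 of those days would be on drug.

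**The case against.** The strongest defence is that the protocol does not stop anyone from acting. Unscheduled tests are not forbidden. Section 17.0 has the PI review safety data continually, Section 16.6 contemplates repeat testing of abnormal results, and Section 7.0 already permits discontinuation at these levels. A mandatory 2-week rule arguably implies the test needed to apply it. All of this stands as a reason to expect that most investigators would retest. None of it requires a retest. The interim reviews after 10, 20 and 30 completers are too infrequent to help an individual subject.

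The retest sentence in 16.8 also lacks its auxiliary verb, so its intent is not certain. As printed, however, symptoms are part of the condition.

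The harm needs several things together: a value of >5 to 8 × ULN that persists beyond 2 weeks, no symptoms or jaundice, bilirubin at or below 2 × ULN, and unused discretion. Entry excludes transaminases above 3 × ULN. Section 2.0 says the data do not support an association between ivacaftor and ALT/AST elevation. With 3:1 randomization, about a quarter of subjects are on placebo. These facts limit the size of the problem but do not remove the gap.

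A reader might infer that the plan mandates no repeat liver test at all. That is not so: Table 1 mandates labs at Days 28, 56 and 84, and what is missing is a triggered test between them. A reader might also take 36 or 56 doses as the possible excess, but the supply limit does not support those figures.

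**Conclusion.** The gap is real and narrow. For an asymptomatic, non-jaundiced subject at >5 to 8 × ULN with bilirubin at or below 2 × ULN, a mandatory stopping rule can go unassessed for about 14 days after it is met (10–18 with ±2, 0–28 with ±7), with at most about 32 extra doses. This assumes that the value persists, that no discretionary test is done, that dosing is twice daily and that there are no left-over tablets.

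The other two liver criteria act on a single result and are unaffected. The documents give no event rate; among about 40 subjects (up to 50 randomized), few would be affected. They do not support a reading that the trial is unsafe or that its conclusions are compromised: power, alpha and the descriptive safety analysis are unchanged. This is a cheap improvement of minor severity.

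**What to change.** Keep the existing rule for symptomatic values above 3 × ULN, supply its missing verb, and add to Section 16.8:

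> Subjects with new ALT or AST >5 × ULN, with or without clinical symptoms, will have repeat testing within 48 to 72 hours and, while the value remains >5 × ULN on study drug, a further test at about day 15 after the first such value.

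Day 15 is named because the criterion is more than 2 weeks. No threshold changes. Weekly testing, or retesting of asymptomatic values of >3 to 5 × ULN, is optional, since no 2-week rule applies in that lower range.

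The cost is about 2 unscheduled draws per flagged subject (day 2–3 and about day 15), each possibly needing an extra visit, or 1 if the first repeat is back at or below 5 × ULN.

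One related matter should be raised separately. Section 7.0 prints the condition "no convincing alternative etiology (e.g., viral hepatitis, alcohol ingestion) for the Elevated transaminase is identified" within its bilirubin bullet, whereas 16.8 applies it to all three criteria. Aligning the two may look editorial. As printed, though, moving the clause would loosen a mandatory discontinuation rule, so it is a substantive decision and not part of this change.
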